### 2. Abstract:

This study will examine cerebrovascular function in older Veterans before and after a proven aerobic exercise intervention, allowing us to better understand the robust impact of exercise on brain function and health. Task-based fMRI and the resultant BOLD map is currently a dominant method of neurocognitive investigation, particularly related to documenting the beneficial changes demonstrated with rehabilitation. No single imaging technique can resolve the complexities of imaging neural plasticity in brain systems, therefore we propose a solution of combining imaging techniques and modeling the impact of perfusion and CVR on the BOLD response. We will model the hypothesized change in perfusion and CVR to the BOLD response following the intervention to quantify the percentage of variance both perfusion and CVR account for in the task-induced BOLD signal. This will allow us to understand the degree to which change in perfusion and CVR impacts the well-documented beneficial change in task-induced BOLD following exercise.

### 3. Background:

The US Census Bureau reports that, of the 18.8 million Veterans of the U.S. armed forces, 9.3 million are age 65 or older. Another 7.7 million fall between the ages of 35 and 65 years of age. Currently the median age for Veterans is around 64 years. As the Veteran population continues to age, the characteristics and comorbidities associated with aging will place a significant financial burden on the healthcare system. According to the Alzheimer's Association, one in three of Veterans over the age of 65 will die with Alzheimer's disease (AD) or a related dementia. Intertwined with aging-related pathologies are physiological changes in cerebrovascular function. In fact, recent epidemiological and clinicopathological data indicate considerable overlap between cerebrovascular dysfunction in aging and AD. While AD is an overt pathology, its time in a "sub-clinical" stage appears be years or even decades before the crossing of a diagnostic threshold. This sub-clinical stage spans a significant amount of time and provides a significant opportunity to initiate targeted interventions for limiting vascular dysfunction in older, at-risk Veterans.

It has been demonstrated that of all modifiable risk factors for AD, decreasing sedentary behavior is the most statistically significant and effective measure to counter the disease processes and associated cognitive decline in older adults. Nearly a quarter million cases of AD would be prevented in the US alone by improving the cardiovascular fitness profile in older adults. This staggering number is an exciting target not only for prevention but also as a means to better understand aging processes and underlying mechanisms malleable to exercise. Equally significant, this number probably underestimates the total impact of increasing cardiovascular fitness due to its effects on other risk factors in aging, including hypertension and obesity.

Two significant goals that are critical to VA RR&D and the aging Veteran population will be achieved with this study. First, this study will define the impact of aerobic exercise on cerebrovascular health in aging Veterans. Decreased vascular health because of aging, and particularly sedentary aging, fosters both cognitive and motor dysfunction and, as noted, has implications for neurodegenerative disease. We do know that older adults who are physically active have improved vascular health but we do not know the impact of an exercise intervention on cerebrovascular health. We will fill this gap by examining changes in basal cerebral perfusion and CVR in older Veterans following a proven cardiovascular fitness intervention. If our hypotheses of improved perfusion and CVR is supported it would inform current intervention strategies and would add important new information about the potential of exercise to improve brain health in aging. This would have immediate implications for aging Veterans at risk for neurodegenerative disease brought on by cerebrovascular dysfunction.

Secondly, this study will advance the current state of literature regarding the beneficial impact of exercise on brain health and function. Research over the last few decades have driven the continual promotion of exercise as one of the most impactful interventions of central nervous system health and function. At the forefront of much of this research is the use of task-based fMRI BOLD to quantify beneficial changes in cortical function following aerobic exercise. While transformative, the true impact of this research is limited in scope until we can define the influence of cerebrovascular function on the well-documented beneficial change in BOLD response. Because the BOLD signal reflects the health and function of the cerebrovasculature, we believe the changes brought on by exercise are at least partially mediated by improved perfusion and CVR. Our statistical model in Aim 3 will allow us to quantify the impact of perfusion and CVR on the BOLD signal during task.

### **Decreased Cerebral Perfusion in Aging**

The brain uses approximately 20% of available oxygen for normal function, making tight regulation of blood flow and oxygen delivery critical for survival. This high demand coupled with a lack of energy stores within the cortex necessitates that cerebral perfusion be constantly and consistently maintained. In a normal physiological state, total blood flow to the brain is remarkably constant, however, with advancing age basal perfusion declines by roughly 4 mL/min per year. It is presumed reactive oxygen species in the cerebrovasculature decreases NO bioavailability leading to the gradual

decline in endothelial function and subsequently perforating arteries, arterioles and capillaries. Ultimately, extracellular matrix components lose elasticity causing decreased vessel function and decreased blood flow.

Morphological studies demonstrate age-related degradation in perfusion throughout the intracranial vessels, however decreased cerebral perfusion is most notably amplified in the frontal cortex. While age-related decline in cerebral perfusion is not great enough to cause major ischemic injury, it results in hypoperfusion that prevents sufficient nutrients from reaching areas of high-metabolic demand such as the frontal cortex. Our own data, presented below, demonstrate a decline in basal cerebral perfusion in the inferior frontal gyrus (IFG) and motor cortex in older adults when compared to younger adults. Of note, the decreased blood supply and inadequate delivery of nutrients is instrumental in age-related cognitive decline, specifically with cognitive executive processes partially mediated by the frontal cortex.

### **Decreased Cerebrovascular Reactivity in Aging**

In addition to blood flow, the dynamic parameter of CVR has a critical role in cerebrovascular health and function. The cerebrovasculature must maintain blood flow within precise limits during rest, activity, disease or injury. In healthy individuals, perfusion is tightly regulated to meet the metabolic demands of the brain via vasoconstriction or vasodilation. Thus, the ability of cerebrovasculature to dilate in the face of increased demand is vital for cerebral function. However, the vasoreactive properties and vascular response to demand have repeatedly been demonstrated to degrade with age and neuropathology. To quantify the efficiency of cerebrovascular response, the degree of vasodilation in response to CO2, a vasoactive agent, is measured. Decreased responsiveness to CO2 is an accepted marker of CVR dysfunction and has been demonstrated to be sensitive to changes brought on by aging.

While the physiologic mechanisms that take place in the human cerebrovasculature resulting in neural decline are as yet unexplained, extensive work in the periphery demonstrates that age-related arterial stiffening and endothelia dysfunction play critical roles in the development of CVR dysfunction. Impairment of the oxidative stress response and dysfunctional inflammatory pathways feed a cascade of age-related CVR malfunction causing increased reactive oxygen species and reduced NO. Together the increase in reactive oxygen species levels and decreased NO suppresses the response of immune cells causing systemic vascular endothelia dysfunction. Behaviorally, decreased CVR has been observed in cognitive decline demonstrated in aging as well as dementia.

### **Impact of Exercise on Cerebrovascular Reactivity**

Aerobic exercise has consistently been associated with enhanced flow-mediated dilatation in the brachial artery of older adults. In the cortex, vasodilatation of the cerebrovascular in response to a CO2 challenge is associated with maximal aerobic

capacity in both young and old adults. Thus, in both the periphery and in the cortex, those with higher levels of cardiovascular fitness have improved CVR to stimulus. CVR was also shown to increase among stroke survivors after six months of aerobic training. Our own pilot data demonstrate marked decline in CVR with age. However, the degree of CVR decay is lessened in older adults that have high levels of self-reported aerobic activity.

### **Link Between Cerebral Perfusion, CVR and Task-Based fMRI BOLD Response**

Seminal studies have continually demonstrated that sedentary individuals who undergo exercise intervention demonstrate BOLD activity that coincides with improvements in an array of tasks in both motor and cognitive domains. While the accessibility and ease of implementation have made BOLD a valuable tool, its interpretation is not straightforward. BOLD is a convoluted neurovascular signal that arises due to the interplay between changes in blood flow and metabolism in response to inhibitory/excitatory causing stimulus. Task-induced BOLD change ( $\Delta$ BOLD) is measured relative to baseline BOLD signal, which means that baseline physiology (blood flow and perfusion) affects the task-induced  $\Delta$ BOLD particularly in magnitude. We believe improvements in these baseline physiological factors are at least partially responsible for the well-documented, exercise-induced BOLD change. As noted, precise levels of blood flow depend on the health of the blood vessels that carry them. The blood carries important nutrient such as glucose and oxygen to support cellular energy demands, thus the amount of baseline perfusion is an indirect measure of tissue baseline metabolic demand. It should be noted that perfusion is a proxy for baseline neural activity, as increased neural activity results in increased demand for blood flow. Further, the blood vessels must dilate in response to an increased demand for blood flow. CVR is an index of baseline vascular health that is necessary to support efficient cerebral perfusion. Thus, to isolate the issue of vascular 'plumbing' versus lower baseline neural activity, we would need to quantify both perfusion and CVR. Taken together, for a better interpretation of task-induced  $\Delta$ BOLD, it is important to understand the relationship between baseline cerebral physiology (perfusion and CVR) and task-induced  $\Delta$ BOLD. To better understand the literature highlighting BOLD alterations following exercise, it is critical to quantify the impact of baseline physiologic measures, including perfusion and CVR on task-induced BOLD changes. We plan to accomplish this task by modeling the contributions of perfusion and CVR to  $\Delta$ BOLD response both before and after the intervention.

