### **Statistical Analysis for Specific Aim 3**

The task fMRI BOLD images will be processed for slice-timing correction, and each image volume will be corrected for rigid-body head motion. The volume registered images will be inspected for artifacts induced by motion, cardiac pulsation and respiratory cycles and removed spatio-temporally using Independent Component Analysis (ICA). These artifact-free images will then be spatially transformed to MNI space using linear and non-linear co-registration algorithms. Following this spatial transformation, the images will be smoothed within the brain to increase the signal-to-noise ratio. Then the images will be scaled to accurately determine the relative percent signal change in BOLD induced by the task. Finally, task-induced BOLD changes ( $\Delta$ BOLD) from pre- to post-aerobic intervention and corresponding hemodynamic response functions are quantified using deconvolution technique.

Since the goal of this aim is to quantify the impact of baseline physiologic measures (ie, resting blood flow and CVR) on task-induced BOLD changes, we plan to accomplish this task by modeling the contributions of perfusion and CVR to  $\Delta$ BOLD responses. The equations below describe our simple modeling approach using linear regression:

$$\Delta BOLD_{i,ROI} = A + B \cdot CBF_{i,ROI} + C \cdot CVR_{i,ROI} + D \cdot (CBF_{i,ROI} \times CVR_{i,ROI})$$

Where subscript  $i$ =pre or post session, ROI refers to the regions of interest, and coefficients A is the modeled intercept, B and C are modeled slopes for perfusion and CVR contributions, and D is modeled slope for the interaction between perfusion and CVR respectively. We will compare the slopes obtained for pre and post exercise to explore (a) how each of the baseline measures (ie, perfusion and CVR) change in response to exercise, and (b) within each condition (pre or post), disentangle perfusion and vascular influence on task-induced BOLD change. Also, modeling for the interaction will account for the coupling effect which by itself can provide insightful information in terms of exercise-induced perfusion-CVR coupled effects. We plan to carry out the

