above processing and modeling at the ROI level as it renders more detection power and is computationally less intensive. From a statistical standpoint, we will compute the F score to test the significance of overall fitting of the model, and we will also obtain the  $t$  score for each predictor (perfusion and CVR) to test the significance of their association with change in measured variable ( $\Delta$ BOLD). To evaluate responsiveness to training and its impact on the model, post hoc analysis will include stepwise multiple regression to evaluate delta VO2 on perfusion and CVR in a-priori ROIs as well as behavioral outcomes.

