### **Power Analysis and Sample Size**

For Aim 1, we used preliminary data comparing older active adults to older sedentary adults. Effect size for difference in inferior frontal perfusion for a small sample ( $n=10$ ) was  $d=2.740$ . If this effect size is taken as an estimate of the effect size for change in the Spin group with  $n=44$  and  $\alpha$  FDR-corrected to 0.0261, then power approaches 1.00. A more conservative estimated change in perfusion being half the effect, with the standard deviation remaining constant, would produce an effect size of 1.370. With the same  $n$  and  $\alpha$  as above, the power still approaches 1.00. The required effect size to achieve a power of 0.80 would be  $d=0.5$ , which would seem quite achievable given our preliminary data. Hence, the power should be more than adequate and seems plausible based on what we know. Because we want to maintain sensitivity at this level, the study is powered mainly to this Aim, while power for Aims 2 and 3 is more than adequate. For

example, for Aim 3, with  $\alpha < .05$ , minimum power of 0.80 and 88 subjects, we have the power to detect an increase in  $R^2$  as small as 0.111 in each ROI. We have detected significant correlations between BOLD response in M1 and IFG with smaller sample sizes (n=36 and n=41, respectively). Accounting for much less than 11% of the variance in criterion variables with the predictors would be too little variance to provide information useful for the design of future clinical trials. Hence, we should have the power to detect effects large enough to impact future clinical trials.

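### Aim 3's product term measures moderation, not perfusion–CVR coupling, and its t tests assign shared explained variance to neither predictor; the joint test is unaffected

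*Combined protocol and SAP*

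**What the plan says.** Section 7, Statistical Analysis for Specific Aim 3, sets out one linear regression per region of interest and session. ΔBOLD is regressed on CBF (coefficient B), CVR (C) and CBF × CVR (D). The plan defines the last coefficient thus: "D is modeled slope for the interaction between perfusion and CVR respectively". It then gives it a further role: "modeling for the interaction will account for the coupling effect which by itself can provide insightful information" about coupled effects of exercise on perfusion and CVR.

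The same section tests the whole model with an F score and adds a t "score for each predictor (perfusion and CVR) to test the significance of their association with change in measured variable" (ΔBOLD). One declared purpose of the modelling is to disentangle perfusion from vascular influence within each session.

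The Abstract says the study will "quantify the percentage of variance both perfusion and CVR account for in the task-induced BOLD signal". The Aim 3 hypothesis in section 4 is joint: perfusion and CVR together explain a significant part of BOLD variability before and after the intervention.

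The Background, under the link between perfusion, CVR and BOLD, states "CVR is an index of baseline vascular health that is necessary to support efficient cerebral perfusion". It says both must be measured to tell a vascular cause from lower baseline neural activity.

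For Aim 3, Power Analysis and Sample Size states "minimum power of 0.80 and 88 subjects, we have the power to detect an increase in" R² "as small as 0.111 in each ROI".

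**The concern.** Two different quantities can be called coupling. One is how closely CBF and CVR track each other across participants. The other is whether they act non-additively on ΔBOLD. D addresses only the second. It can be zero when CBF and CVR are strongly correlated, and non-zero when they are unrelated. The plan specifies no CBF–CVR correlation, no regression of one on the other and no mediation model, so the first quantity is never estimated. A moderation coefficient could then be reported as exercise-induced coupling.

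The second problem holds whichever meaning was intended. If CBF and CVR are correlated, each t test sees only what that predictor explains beyond the other. Variance that they explain in common enters the overall F and R² but neither t test, and D does not recover it. A model could be significant overall while both predictors look unimportant. A reader could then take a non-significant t to mean no contribution. The stated wish to separate the two influences is what suffers.

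**Working it through.** **Inputs from the plan.** N = 88, α = 0.05, power 0.80 and a detectable R² increase of 0.111 per region (Power Analysis and Sample Size). The numerator degrees of freedom are not stated.

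**Reproducing the plan's figure.** f² = R²/(1 − R²) = 0.111/0.889 = 0.125. The noncentrality is λ = N·f² = 88 × 0.125 ≈ 11.0. From the noncentral F with 88 − 3 − 1 = 84 denominator df:

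- 3-df overall test (CBF, CVR, product): power 0.783
- 2-df test: 0.839
- 1-df test: 0.906

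The R² that gives exactly 0.80 is 0.115, 0.102 and 0.084 respectively. Read as R², 0.111 fits the 3-df overall test to within two points. If 0.111 were instead f², a 2-df test would give 0.791. Either way the figure describes a multi-predictor test, not a test of one predictor.

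**What D responds to.** With no true moderation and n = 200,000 simulated participants, the fitted D was 0.00 at CBF–CVR correlations of 0, 0.5 and 0.9. D carries no information on how closely the two measures track each other.

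**Splitting the explained variance.** Assume equal standardised slopes b, centred predictors, no true interaction, and CBF–CVR correlation r:

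- Total: R² = 2b²(1 + r)
- Unique to each: U = b²(1 − r²)
- Shared: R² − 2U = 2b²(1 + r)r, so shared/R² = r

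Example at r = 0.5: b² = 0.111/(2 × 1.5) = 0.0370; U = 0.0370 × 0.75 = 0.0277; shared = 0.111 − 2 × 0.02775 = 0.0555, half of the total.

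For one t test, λ = 88 × U/0.889. At r = 0.5, λ = 88 × 0.02775/0.889 = 2.75.

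The documents give no r, so the table shows a range, including zero:

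| r (assumed) | Unique R², each | Shared R² | λ, one t | Power of one t, formula | Power of one t, simulated | Neither t significant, given F significant |
|---|---|---|---|---|---|---|
| 0 | 0.0555 | 0 | 5.49 | 0.639 | 0.62 | 2% |
| 0.3 | 0.0388 | 0.0333 | 3.85 | 0.492 | 0.48 | 8% |
| 0.5 | 0.0277 | 0.0555 | 2.75 | 0.374 | 0.37 | 21% |
| 0.7 | 0.0167 | 0.0777 | 1.65 | 0.245 | 0.23 | 43% |

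The overall F keeps the same power in every row: 0.783 by formula, about 0.77 in simulation. Repeat simulations agree within about two percentage points.

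The r = 0 row matters. Power of one t test is already about 0.62 there, because R² of 0.111 is split between two predictors. The loss due to correlation is the further fall: 0.62 − 0.48 = 0.14 at r = 0.3 and 0.62 − 0.23 = 0.39 at r = 0.7.

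**The case against.** The coupling half rests on one sentence. D is introduced in a regression whose outcome is ΔBOLD, so coupled effects may simply mean a joint, non-additive effect on ΔBOLD. D is then the right coefficient and only the wording is at fault. This stands. The documents do not settle which meaning was intended.

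A reader might infer that the promised percentage of variance cannot be obtained, or that the Aim 3 hypothesis cannot be tested. The documents do not support that. The Abstract and section 4 can both be read jointly, and the overall R² and F include the shared part.

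A reader might also infer that the trial would fail an objective by missing a change in coupling. No aim or hypothesis promises to estimate a CBF–CVR association, and the comparison of slopes between sessions is described as exploratory. One can simulate a rise in r from 0.2 to 0.6 under an additive BOLD model and find that comparing D detects it only 5% of the time. That result is built in, because true D is zero in both sessions. It illustrates the definition of D and does not measure harm.

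Partial coefficients are a standard way to separate two influences, and a unique contribution is a legitimate estimand. A variance split labels the shared part without assigning it. This also stands, but the split shows how much of the explained variance the t tests leave out.

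Finally, the Background calls CVR necessary for efficient perfusion; it does not say that the two correlate across participants, and it treats them as distinct constructs. A large r is therefore an assumption.

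**Conclusion.** The concern holds in a limited form. D measures moderation of the CBF–BOLD slope by CVR; it neither estimates the CBF–CVR relation nor adjusts for it. The t tests show unique contributions only. The joint Aim 3 hypothesis and the joint percentage of variance are intact. At risk are the goal of separating the two influences and any statement about coupling.

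The size depends on r. With little correlation the practical loss is small: neither t is significant in about 2% of F-significant trials at r = 0 and 8% at r = 0.3. It becomes material at r = 0.5 (21%) and r = 0.7 (43%). These figures assume R² = 0.111, N = 88, equal slopes, no true interaction and centred predictors. The plan does not mention centring. Without it, B and C are slopes at zero CVR and zero CBF, and their t tests mean something else.

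**What to change.** In Statistical Analysis for Specific Aim 3:

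1. Describe D as moderation, that is, a non-additive joint effect of perfusion and CVR on ΔBOLD, and drop the word coupling for it. State that both predictors are centred.
2. If coupling is to be reported, estimate the CBF–CVR association directly in each region and session. Compare sessions with a paired or bootstrap test, since the same participants contribute to both, and label this exploratory.
3. Beside the t tests, report the overall R² with its unique-CBF, unique-CVR and shared parts and bootstrap intervals. State that a non-significant t will not be read as no contribution.

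The cost is a few extra regressions per region on data already collected, plus revised wording. The shared part will still belong to neither predictor, but its size will be visible.
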